Domain-Specific Appendix: Metformin

Strategies to Promote ResiliencY (SPRY)-
An Adaptive Randomized Clinical Trial of
Metformin in High Risk Surgical Patients

**UPMC REMAP: Randomized, Embedded,
Multifactorial Adaptive Platform Trial for
Optimizing Surgical Outcomes**
NCT 03861767

IRB approved January 17, 2020

Summary

In this domain of the UPMC REMAP trial, participants with elective surgery at UPMC facilities will be randomized to receive the following Metformin doses or placebo:

- Placebo
- 500mg ER daily
- 1000mg ER daily
- 1500mg ER daily

UPMC REMAP: Metformin Duration Domain Summary	
Interventions	
 • Placebo • 3 different doses of Metformin, • 3 different pre-operative dosing durations: short (7-28 days), intermediate (29-90 days); long (over 90 days) • Metformin continued for 90 days after surgery
Strata	Analysis and Response Adaptive Randomization are by strata (surgical type) to allow for strata-by-intervention interaction
Evaluable Interactions	Intervention-intervention interactions will be evaluated between interventions in this domain and the complimentary interventions in the ERAS Domain
Timing of Reveal	Randomization with Immediate Reveal and Delayed Initiation (with reveal and initiation only occurring after consent or agreement for participation is obtained)
Inclusions	Patients are eligible for this domain only if they have been included in the Master Protocol inclusion criteria
Domain-Specific Exclusions	
Domain exclusions:
 
 • The treating clinician believes that participation in the domain would not be in the best interest of the patient • Pre-existing diabetes type I or II • Women of child-bearing potential • Presently taking metformin or prior use in the past 6 months • Evidence of an absolute or relative contraindication to Metformin therapy 
 ○ Known allergy to metformin ○ Acute or chronic metabolic acidosis with or without coma ○ Hemodialysis, end-stage renal disease, or GFR < 45 in the prior 30 days ○ Ongoing treatment with therapy known to have significant drug-drug interaction with metformin (carbonic anhydrase inhibitors, cimetidine, gliptins) ○ History of lactic acidosis ○ History of excessive alcohol intake ○ Severe hepatic dysfunction
Outcome measures	
Primary REMAP endpoint: hospital free days at day 90 after the surgical encounter
 
Secondary REMAP endpoints refer to Core Protocol
 
Secondary domain endpoints:
 
 1. Gastrointestinal distress causing discontinuation of the medication 2. Lactic acidosis 3. Hepatic dysfunction 
Serious Adverse Events (SAE) as defined in CORE protocol

TABLE OF CONTENTS

1. ABBREVIATIONS	6
2. PROTOCOL APPENDIX STRUCTURE	7
3. Metformin DOMAIN-SPECIFIC APPENDIX VERSION	7
3.1. Version History.....	7
4. Metformin DOMAIN GOVERNANCE.....	8
4.1. Domain Members	8
4.2. Contact Details.....	10
5. Metformin DOMAIN-SPECIFIC WORKING GROUP AUTHORIZATION	11
6. BACKGROUND AND RATIONALE	11
6.1. Domain Definition	11
6.2. Domain-specific Background	11
6.2.1. Guideline Recommended Use of Metformin and Potential Applications	12
6.2.2. Metformin Mechanisms of Action.....	13
6.2.3. Association of Metformin with Longevity in Small Clinical Trials	13
6.2.4. Metformin Safety Profile	13
7. DOMAIN OBJECTIVES	14
8. TRIAL DESIGN	15
8.1. Population.....	15
8.2. Eligibility Criteria	15
8.2.1. Inclusion Criteria for this Domain	15
8.2.2. Exclusion Criteria from this Domain	15
8.3. Interventions	16
8.3.1. Research Testing	16
8.3.2. Study Drug Intervention.....	16
8.3.3. Timing of Initiation of Intervention.....	17
8.3.4. Duration of Administration of Study Drug	17
8.3.5. Temporary Suspension of Study Drug.....	17
8.3.6. Suspension of Study Drug at the Direction of the Treating Clinician.....	17
8.3.7. Collection of Blood Samples	18
8.3.8. Collection of Samples for Microbiome Sub-study	18
8.3.9. Collection of questionnaires	19

8.3.10. Muscle Biopsy Sub-Study	21
8.4. Endpoints	23
8.4.1. Primary Endpoint	23
8.4.2. Secondary Endpoints.....	23
9. TRIAL CONDUCT	24
9.1. Domain-specific Data Collection	24
9.1.1. Clinical Data Collection	24
9.2. Criteria for Discontinuation	24
9.3. Blinding	24
9.3.1. Blinding	24
9.3.2. Unblinding.....	24
10. STATISTICAL CONSIDERATIONS.....	24
10.1. Domain-specific Stopping Rules.....	24
10.2. Strata.....	25
10.3. Timing of Revealing of Randomization Status	25
10.4. Interactions with Interventions in Other Domains	25
10.5. Post-trial Sub-groups.....	26
11. ETHICAL CONSIDERATIONS	26
11.1. Data Safety and Monitoring Board	26
11.2. Potential Domain-specific Adverse Events	26
11.3. Domain-specific Consent Issues.....	26
12. GOVERNANCE ISSUES	27
12.1. Funding of Domain.....	27

1. ABBREVIATIONS

eGFR: estimated Glomerular Filtration Rate

ERAS: Enhanced Recovery after Surgery

GFR: Glomerular Filtration Rate

2. PROTOCOL APPENDIX STRUCTURE

The structure of this protocol is different to that used for conventional trials because this trial is highly adaptive and can best be described as 'modular' in its protocol design. With competing treatment interventions nested within a domain, both interventions and domains will change over time. While all adaptations are pre-specified, the structure of the protocol is designed to allow the trial to evolve over time, for example, by the introduction of new domains or interventions or both and commencement of the trial in new clinics.

The protocol has multiple modules, in brief, comprising a Core Protocol (overview and design features of the study) and multiple Domain-Specific Appendices (DSA) (detailing all interventions currently being studied in each domain).

The Core Protocol contains all information that is generic to the trial, irrespective of the clinic in which the trial is conducted and the domains or interventions that are being tested. The Core Protocol is void domain and intervention specifics, statistical analysis plans, and simulation specifics. The Core Protocol may be amended, but it is anticipated that such amendments will be infrequent.

Information about the intervention(s) to be examined, within each domain, is covered in a DSA. These Appendices are anticipated to change over time, with removal and addition of options within an existing domain, at one level, and removal and addition of entire domains, at another level. Each addition of a new domain and/or new intervention to an existing domain in a DSA will be subject to a separate ethics application for approval.

Although the analysis model will change over time in accordance with the domain and intervention trial adaptations, this information is contained in the Statistical Analysis and Simulations Appendices. Each modification will be subject to approval from the Trial Steering Committee (TSC) in conjunction with advice from the Data Safety and Monitoring Board (DSMB).

3. METFORMIN DOMAIN-SPECIFIC APPENDIX VERSION

The version of the Metformin Domain-Specific Appendix is in this document's header and on the cover page.

3.1. Version History

Version 1: Proposed on 16 July 2018

Version 2: Proposed on 20 January 2019

Version 3: Proposed on 25 June 2019

Version 4: Proposed on 17 July 2019

Version 5: Proposed on 31 July 2019

Version 6: Proposed on 15 October 2019

6. BACKGROUND AND RATIONALE

6.1. Domain Definition

This is a domain within the UPMC REMAP to test the effectiveness of different doses and durations of metformin in nondiabetic patients with elective surgical encounters at UPMC who meet eligibility criteria.

6.2. Domain-specific Background

Our population is aging. Aging is associated with altered inflammatory and immune responses. This altered response has been termed “inflammaging”, and has been attributed to age-related diseases and treatment complications. Surgical stress is less well tolerated in older patients. Therapies aimed at pre-habilitation and ameliorating the response of individuals to such stressors hold the promise of improving outcomes in patients undergoing operative procedures. Pharmacological pre-habilitation possesses the potential of altering the response of older and at risk individuals towards that of younger and healthier individuals. Metformin is one such therapy based on a combination of exciting pre-clinical and clinical data demonstrating enhanced longevity and a pleiotropic modulation of inflammatory response.

6.2.1. Guideline Recommended Use of Metformin and Potential Applications

Metformin is considered first line therapy for patients with type II diabetes mellitus with hyperglycemia that cannot be controlled with lifestyle alone. Unlike other oral medications, metformin is favored for its insulin sensitizing effects resulting in improved glycemic control, weight loss, and overall improvement of metabolic syndrome. Over the past fifteen years, metformin has received significant attention for its other potential therapeutic uses and has been found to decrease the rate of age related illness progression improving longevity, especially in the setting of cancer. Additionally, recent clinical trials across multiple disease states have shown metformin to decrease all-cause mortality in diabetic and non-diabetic patients ¹⁻³. Although the mechanisms by which metformin affects longevity is an active area of both basic science and clinical research, it clearly has anti-inflammatory properties both independent and dependent of glycemic control ⁴.

6.2.2. Metformin Mechanisms of Action.

The underlying mechanisms of action of metformin are under active investigation. A leading hypothesis is that cellular mitochondria are the primary site of metformin in activity. Metformin decreases intracellular AMP and increases 5'-AMP-activated protein kinase (AMPK) resulting in three main downstream effects². First and foremost, there is a decrease in gluconeogenesis, decreasing serum glucose levels, and improving insulin resistance. Secondly, mitochondrial AMPK activation inhibits mechanistic target of rapamycin (mTOR), which decreases mitotic activity and therefore has anti-tumor affects influencing mitochondrial homeostasis. Finally, downstream protein synthesis inhibition results in decreased production of both pro-inflammatory cytokines and reactive oxygen species (ROS) through activation of the thioredoxin antioxidant system decreasing DNA damage^{2,4,11,12}. The anti-inflammatory effects of metformin, in addition to glycemic control, are thought to be the leading cause of the proposed anti-aging and cardiovascular protection of metformin¹¹. While this clinical benefit is established in diabetic patients, the anti-inflammatory mechanism of action is, at least in part, independent of glycemic control. Therefore, as in prevention and treatment of cancer, metformin has properties that can help control inflammation in all patients with systemic inflammation.

6.2.3. Association of Metformin with Longevity in Small Clinical Trials

Recently, there have been multiple prospective clinical trials exploring the effect metformin in non-diabetic and diabetic patients. Patients were treated with standard clinical doses of metformin ranging from 250mg-2000mg three times days from 14 days to 48 weeks continuing to demonstrate an excellent safety profile. The metformin was very well tolerated with the primary side effect (30-60% of subjects) was self-limited gastrointestinal discomfort including mild diarrhea and anorexia^{1,13,14}. Across multiple disease states, metformin has been shown to decrease appetite stimulating glucagon like peptide-1, decrease low density lipid profiles, decrease the mitotic rate in breast cancer, and improve liver pathology in patients with non-alcoholic steatotic hepatitis^{1,3,13,15-17}. As discussed above, some of these changes are attributed to the anti-glycemic and anti-tumor effects of metformin, yet the anti-inflammatory role cannot be underestimated. However, the effects of metformin on non-diabetics and longevity remain unexplored.

6.2.4. Metformin Safety Profile

The safety profile of metformin is well established. However, there are also safety concerns regarding metformin with reports of hepatic damage and lactic acidosis, although these are

rare. More commonly, metformin can cause diarrhea and other gastrointestinal-related adverse effects, taste disturbances, headaches and muscle weakness.

7. DOMAIN OBJECTIVES

The objective of this domain is to determine the effectiveness of different doses and durations of metformin in select patients evaluated prior to elective surgery at UPMC.

The interventions that will be compared are:

- Varied doses of metformin (500, 1000, and 1500mg ER) started at the pre-operative clinic before elective surgical encounter at UPMC vs. placebo with continuation for 90 days post-op
- Varied pre-op duration of metformin (short-7-28 days; intermediate-29-90 days; and long-90+ days) as dictated by the individual's clinical course

We hypothesize that the elective surgical patients will experience more hospital free days at day 90 after the surgical encounter after administration of metformin vs. placebo.

We hypothesize that longer course of metformin will lead to more hospital free days at day 90 after the surgical encounter compared to a shorter course.

We hypothesize that the higher dose of metformin will lead to more hospital free days at day 90 after the surgical encounter compared to lower doses of metformin or placebo, and the effect will depend on the type of surgical procedure (and corresponding inflammatory insult). This is termed a strata-by-intervention interaction.

We hypothesize that metformin treatment will alter the complexity and diversity of the microbiome as compared to placebo (microbiome sub-study).

We hypothesize that metformin treatment will alter muscle strength as compared to placebo (Motor Assessment Group).

We hypothesize that metformin treatment will alter striated muscle fiber structure (Muscle Sub-Study) and correlate with decreased muscle strength as compared to placebo (Motor Assessment Group).

8. TRIAL DESIGN

This domain will be conducted as part of a UPMC REMAP trial for Optimizing Surgical Outcomes.

Treatment allocation will be adaptive, as described in the Core Protocol.

8.1. Population

The REMAP enrolls patients with elective surgical encounters admitted to UPMC facilities. Up to 2000 patients will be enrolled.

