8.2.1. Inclusion Criteria for this Domain

Patients are eligible for this domain only if they have been scheduled for elective surgery at UPMC facilities and are being evaluated pre-operatively prior to surgery.

Other criteria include:

- Age \geq 60 years
- Age < 60 but evidence of comorbidity risk as represented by a Charlson Comorbidity Index of > 2 in 12 months prior to enrollment
- Able to take an oral medication in non-crushable pill form
- Women must be post-menopausal, which is defined as not having a menstrual period within the last 12 months

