8.3.3. Timing of Initiation of Intervention

The intervention is to begin on the day following the evaluation of the eligible and consented subject at the pre-operative clinic/surgeon's office. Daily oral doses will continue through the hospital admission for elective surgery. For patients without side effects, dosing will continue daily for 90 days after the surgical encounter.

Patients will be contacted between the pre-operative clinic/surgeon's office visit and surgery to evaluate study drug compliance as well as any adverse events associated with the study drug.

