## **8. ANALYSIS POPULATIONS**

All participants who were randomized and underwent a surgical intervention within 365 days of randomization will be considered in our analysis population.

- SPRY intention to treat (ITT): This population consists of all patients enrolled and randomized to any treatment dose and duration. This population will only include those who underwent a surgical intervention at any time in the 365 days following randomization. All comparisons will be made based up the randomization table allocated treatment.
- SPRY per protocol analysis (PPA): This population consists of all patients enrolled and randomized who also completed randomization table allocated treatment and underwent a surgical intervention within 365 days of enrollment. Adherence to the protocol is determined by those who confirmed compliance with study drug at their 90-day postoperative evaluation with the study team. Compliance is defined by the verbal confirmation of study drug completion at the 90-day follow up timepoint.

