### 9.1. Primary Endpoint

The primary endpoint for this domain is the REMAP primary outcome of hospital free days at 90 days after the index date (HFD-90). The index date for HFD-90 outcome is defined as the date of the elective surgical encounter.

Hospital free days Score	Score
-1	Patient died during surgery or within the 90 days following their surgical intervention
0	No days out of the hospital in the 90 days following the surgical intervention
1-90	One to 90 days out of the hospital and alive in the 90 days following the surgical intervention

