### 13.1. Primary Analysis of Primary Endpoint

#### *Primary Analysis*

The **primary analysis model** is a Bayesian cumulative logistic model for the ordinal primary endpoint. The primary analysis is to be completed in both the ITT and PPA populations described above.

In the primary analysis, observations will be pooled across pre-operative duration of study drug and will borrow across study drug dose. The primary endpoint for this model is HFD-90 and will be compared across the placebo and three levels of study drug dose. The general Bayesian cumulative logistic model is defined below:

Throughout we assume for patient  $i$ ,  $y_i$  is the observed 90-day HFD,  $g(i)$ , is the surgical strata from 1:G,  $d(i)$  is the pre-op duration from 1:3 with 1 = short, 2 = intermediate, and 3=long, and  $t(i)$  is the intervention from 1:4 with 1 = placebo, 2 = 500mg, 3 = 1000mg, and 4 = 1500mg.

The general Bayesian ordinal logistic regression model is used to estimate the effect of dose and duration of metformin on the distribution of HFD-90 under placebo adjusting for expected differences given the surgical strata. The ordinal scale parameterization is a generalized version of the dichotomous parameterization where we model all cumulative probabilities of 90-day HFD being less than or equal to a cutpoint  $c$ , where  $c = -1, \dots, 89$ . Given each cutpoint  $c$ , we denote the 91 dichotomized versions of 90-day HFD for patient  $i$  as  $\gamma_{c,i}$  where  $\gamma_{c,i} = 1$  if 90-day HFD is in  $[-1, c]$  and  $\gamma_{c,i} = 0$  if 90-day HFD is in  $[c+1, 90]$  for  $c = -1, \dots, 89$ .  $\gamma_{c,i}$  is then modeled throughout as:

$$\gamma_{c,i} \sim \text{Bernoulli}(\phi_{c,i});$$

$$\text{logit}(\phi_{c,i}) = \gamma_c + \mu_i;$$

where  $\mu_i$  is a patient-specific mean function and  $\gamma_c$  is common across all patients. To assure model stability, if there is an outcome in the ordinal scale that did not occur in the data, then that outcome will be combined with a neighboring outcome (the worse outcome). For example, if the outcome 11 never occurred, then a combined outcome of 10 & 11 will be modeled for the analysis.

The subject-specific mean function is as follows:

$$\mu_i = \alpha_{g(i)} + \theta_{t(i), d(i)}.$$

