### **13.3. Subgroup Analyses**

For the primary outcome of HFD-90 only, subgroups will be evaluated using a frequentist cumulative logistic regression model, as in the primary analysis. These analyses will be conducted on both the ITT and PPA populations and will follow the same approach to pooling across duration and borrowing across dose as in the primary analysis. Analyses will be stratified by each of the following subgroups:

1. Age >= overall median vs < overall median (hypothesis, more effective among those > median)
2. Sex at birth (hypothesis: no difference)
3. Frailty, comparing robust/normal vs. frail/very frail (hypothesis, more effective among frail and very frail). Note that subgroup of robust with normal and frail with very frail may be modified as necessary (e.g., to robust vs. normal/frail/very frail) if sample size for either group is <= 25).
4. Surgical strata (hypothesis, no difference)
  - o No operation
  - o Spine
  - o General surgery/surgical oncology
  - o Colorectal Surgery
  - o Other
  - o Any strata with <= 25 subjects will be combined into the "Other" category, except the "No operation" group
5. Surgical stress (hypothesis, more effective among higher stress procedures)
  - o Same day surgery procedures
  - o Procedures with subsequent hospital admission

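### The primary HFD-90 model pools same-day and admitted surgery with no term for planned setting, so any real metformin effect is read closer to 1 and with less power

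*Protocol*

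**What the plan says.** **Population.** Protocol 8.1 states: "The REMAP enrolls patients with elective surgical encounters admitted to UPMC facilities". Protocol 8.3.3 also presumes a stay: "Daily oral doses will continue through the hospital admission for elective surgery". The domain inclusion criterion in Protocol 8.2.1 is wider and does not mention admission: "Patients are eligible for this domain only if they have been scheduled for elective surgery at UPMC facilities".

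**Analysis set.** SAP 8 does not restrict by setting: "All participants who were randomized and underwent a surgical intervention within 365 days of randomization will be considered in our analysis population". SAP 13.3 plans a surgical-stress subgroup with two levels, "Same day surgery procedures" and "Procedures with subsequent hospital admission". The SAP therefore expects both kinds of patient in the analysed data.

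**Endpoint.** SAP 9.1 scores death as -1, no days out of hospital as 0, and the rest as "One to 90 days out of the hospital and alive in the 90 days following the surgical intervention". It does not say how the day of surgery or a part-day counts.

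**Model.** In SAP 13.1 the patient-level predictor is a surgical-stratum shift plus the dose/duration effect, described as "adjusting for expected differences given the surgical strata". SAP 7 defines the six strata by specialty and enrolling clinic. The frequentist proportional odds model adjusts for stratum and duration. Neither model has a term for setting.

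**The concern.** A same-day patient who survives and is not readmitted scores at or very near 90. A patient who stays in hospital generally scores lower. Whether a stay was planned is known before surgery and should predict HFD-90 strongly. Specialty is a poor stand-in, because one stratum can hold both kinds of procedure.

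Two things follow if metformin has an effect. First, odds ratios are non-collapsible: leaving a strong prognostic factor out of the model moves the fitted odds ratio toward 1 relative to the value within each setting, even when the factor is balanced between arms. Second, if same-day patients have little to gain, including them dilutes the effect as well. Both reduce the chance of reaching the SAP's posterior probability threshold of 0.975, in a trial that closed before its first 500-patient analysis.

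**Working it through.** The plan states no power, placebo distribution or same-day share, so there is no figure to reproduce. The check asks what the model would return under stated assumptions.

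**Inputs from the documents**
- Odds ratio of interest 0.8, where below 1 means more hospital free days (Protocol 10.1).
- Allocation √3:1:1:1 (SAP 6), so the metformin share is 3/(3 + 1.732) = 0.634.
- One-sided 0.025, or posterior probability above 0.975 (SAP 13).

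**Assumptions**
- Doses pooled; N = 450, chosen as below the first planned analysis at 500.
- Same-day placebo patients: 90% score 90.
- Admitted placebo patients: 3% score 90, or 30% if the counting rule lets short stays reach 90.
- Ten ordered levels for admitted placebo patients, worst to best: 3, 3, 5, 7, 10, 14, 18, 19, 18 and 3%. The 30% case and the same-day group are proportional-odds shifts of this.
- No stratum term until step 4.

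**Step 1. One cutpoint by hand (below 90 versus 90), 40% same-day, true odds ratio 0.8 in both settings**
- Admitted: placebo 0.97, odds 32.33; metformin odds 0.8 × 32.33 = 25.87, probability 0.9628.
- Same-day: placebo 0.10, odds 0.1111; metformin odds 0.0889, probability 0.0816.
- Mixed placebo: 0.6 × 0.97 + 0.4 × 0.10 = 0.622, odds 1.646.
- Mixed metformin: 0.6 × 0.9628 + 0.4 × 0.0816 = 0.6103, odds 1.566.
- Ratio: 1.566/1.646 = 0.95, although it is 0.80 in each setting.
- With 30% of admitted patients at 90, the same steps give 0.734/0.852 = 0.86.

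**Step 2. All cutpoints.** Proportional odds models logit P(Y ≤ c) = γ_c + βT, with and without λS for setting, were fitted by maximum likelihood to expected counts. Power = Φ(|log OR|/SE − 1.96).

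| Same-day share | Admitted at 90 | Benefit in same-day | No term: OR, power | Setting term: OR, power |
|---|---|---|---|---|
| 10% | 3% | yes | 0.83, 19.0% | 0.80, 23.9% |
| 10% | 30% | yes | 0.82, 19.6% | 0.80, 21.5% |
| 40% | 3% | yes | 0.90, 8.8% | 0.80, 19.2% |
| 40% | 30% | yes | 0.85, 13.1% | 0.80, 17.6% |
| 40% | 3% | no | 0.91, 7.6% | 0.83, 15.0% |
| 40% | 30% | no | 0.875, 10.4% | 0.83, 13.5% |

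If the same-day distribution is not a proportional shift of the admitted one, the 40% result with benefit in both settings (3% of admitted patients at 90) is 0.89 without the term and 0.81 with it.

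**Step 3. Ceiling alone.** In one homogeneous population with true odds ratio 0.80, the fit stays at 0.800 whether 3%, 30%, 60% or 90% of placebo patients score 90. Only precision changes: at N = 1000 the standard error rises from 0.115 to 0.227 and power falls from 0.49 to 0.17.

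**Step 4. Does stratum absorb setting?** Take two equal strata with 10% and 70% same-day (40% overall), 3% of admitted patients at 90, and benefit in both settings. The fit is 0.89–0.90 with no covariate, 0.87–0.88 with stratum, and 0.80–0.81 with stratum and setting. Stratum removes only a small part of the shift.

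**The case against.** **The odds ratio that ignores setting is a different estimand, not a biased one.** This is correct. With a true odds ratio of 1 there is no shift and no inflation of false positives. The point concerns power and interpretation.

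**SAP 13.3 already splits HFD-90 by same-day versus admission.** It does, in both analysis populations and with a stated direction, and that deserves credit. But it leaves the primary posterior unchanged, and its second level is worded by what followed the procedure, which treatment could affect.

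**The size is undocumented and the rescue is modest.** This stands. The same-day share, the distribution and the counting rule are all assumed. At an odds ratio of 0.8 the trial would probably miss the effect with or without the term. Larger claims about equivalent sample size need a stronger effect than the protocol's own and cannot be supported.

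**The model was fixed before enrolment, and planned setting is not a listed field.** Planned setting is absent from Protocol 9.1.1 and SAP 11, so it would have to be abstracted. However, SAP 4 shows that the model was already changed after early closure, with 14 surgical types reduced to 6 and three durations to one.

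Three stronger readings are tempting but not supported:
- *The pile-up at 90 pulls the odds ratio toward 1.* Step 3 shows that a ceiling alone costs precision only.
- *Ineligible patients were enrolled.* Protocol 8.1 is a descriptive sentence; the criterion in 8.2.1 asks only for scheduled elective surgery.
- *A setting term restores the full effect.* It does so only if same-day patients benefit equally; otherwise the fit is about 0.83.

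**Conclusion.** The point holds as a matter of efficiency and interpretation. Same-day and admitted procedures share one HFD-90 model that omits a probably strong predictor known before surgery. If metformin works, the reported odds ratio will lie nearer 1 than the effect within either setting when both benefit, or than the effect in admitted patients when only they benefit.

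At an odds ratio of 0.8 and a 40% share with benefit in both settings, between about 29% (1 − ln 0.853/ln 0.8) and 52% (1 − ln 0.899/ln 0.8) of the log odds ratio is lost. Adding the term gains about 5 to 10 percentage points of power at N = 450. At a 10% share the gain is about 2 to 5 points. These figures pool the doses, whereas the primary model estimates each dose with borrowing, so they indicate scale and do not predict this trial's result. The direction is firm; the size cannot be fixed from the documents.

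**What to change.** 1. In SAP 13.1, add planned setting (same-day or inpatient, as scheduled before surgery) to the Bayesian model, μ_i = α_g(i) + λ_s(i) + θ_t(i),d(i), and to the frequentist proportional odds model. Abstract it from the record; do not use the admission that actually happened. Give λ a weakly informative prior wide enough for the likely gap: under the assumptions above the settings differ by logit 0.97 − logit 0.10 = 5.7, or logit 0.70 − logit 0.10 = 3.0, on the log-odds scale.
2. If the prespecified primary model is to be kept, run this as a named sensitivity analysis.
3. Define the SAP 13.3 surgical-stress subgroup by planned setting too, and show the planned-inpatient estimate beside the overall one.
4. Reconcile Protocol 8.1 with SAP 8 and 13.3 by stating whether same-day patients belong to the target population, and report their share.
5. Do this before unblinding, which SAP 5 ties to finalising the plan. If unblinding has passed, label the analysis exploratory under SAP 13.4.

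The cost is one field to abstract, one model term and a few sentences. The odds ratio would then be read as a within-setting effect. If no same-day patients were enrolled, stating so closes the point.
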